### **Secondary outcome measures**

Secondary outcome measures will include the change in:

1. Box and Block Test
2. Modified Ashworth Spasticity Scale for shoulder elbow and wrist joints
3. Shoulder subluxation distance in centimeters
4. Visual Analogue Pain scale to assess shoulder, elbow, wrist, and hand pain.
5. Motor Activity Log (MAL) – Post therapy and Follow-up assessments only
6. Functional Ambulation Category (FAC)
7. Number of exercise repetitions performed with device or exercise program.

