## **Describe the statistical methods for the stated specific aims and hypotheses. The analysis plans should match the stated study specific aims and hypotheses:**

All reported data from this study will be disaggregated by sex to test for any potential bias due to this biological variable. Data will be analyzed using modified intention-to-treat analysis. That is, all participants will be included in the analysis if the follow-up assessment is available, regardless of any deviations from the protocol. The effect of treatment on the primary outcome measure will be assessed using a repeated measures analysis of covariance (RM-ANCOVA) to account for any baseline differences between groups or variability in treatment intensity, with follow-up comparisons performed using Bonferroni-corrected t-tests or Wilcoxon rank sum tests if the data violates the assumption of normality. We hypothesize the participants in the movable wheelchair arm rest device group will have significantly greater and clinically meaningful (i.e. >4.25 FM points) reductions in motor impairment than participants in the control group due to the increased dose of UE motor system activation. Using data from the sensors on movable wheelchair arm rest device, we will test if this effect depends nonlinearly on the number of repetitions performed with the device, consistent with recent meta-analyses of forelimb recovery in a rodent model of stroke. That is, we hypothesize that the movable wheelchair arm rest device will provide a benefit only if the dose exceeds a threshold. A key goal is to also identify that threshold (by making a graph for humans like the one for rats), which will enable us to move forward with effective clinical prescription and goal setting with the movable wheelchair arm rest device. Visual analog pain, spasticity, and FAC scores will also be analyzed using RM-ANCOVA to test for significant changes related to use of the device. All analyses will be reviewed by a statistical consultant in the Institute for Clinical and Translational Science at UC Irvine.

**Provide precise definitions of the study endpoints and criteria for evaluation; if the primary outcomes are derived from several measurements (i.e., composite variables) or if endpoints are based composite variables, then describe precisely how the composite variables are derived:**

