**Describe the statistical method(s) that will be used to analyze the primary outcome(s) or endpoints:**

t-tests with Bonferroni corrections, or Wilcoxon rank sum tests if the distributions fail the Lilliefors test for normality.

**If appropriate describe secondary or post hoc analyses of primary outcome(s) or other exploratory analysis and if necessary, provide a breakdown of the methods used per outcome or endpoint:**

The effect of treatment on each outcome measure will be assessed using a repeated-measures ANOVA

---

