## Provide a detailed chronological description of the procedures:

Participants will be invited for an initial assessment within three days of admission to an IRF to confirm they meet the inclusion criteria and to establish a baseline measure. Those who qualify will be randomly assigned to either the movable wheelchair arm rest device group or the control group. To ensure matched levels of impairment between groups, subjects will be stratified by their FM score into two levels (0-21, 22-42) and then randomized by alternating block allocation based on the time of enrollment. Individuals in the device group will be provided with a wheelchair equipped with movable wheelchair arm rest device and trained how to use it to perform stationary reaching practice and to help them ambulate. Once participants are competent, they will be instructed to perform stationary reaching practice and to use the movable wheelchair arm rest device to ambulate around the inpatient facility, with a target dose of 1000 device "reps" per day, which we estimate will take about 30 minutes of device use at around 1 rep every 2 seconds. The supervising therapist will customize the range of motion needed for device's integrated electronics to count a "rep" based on each patient's abilities. Participants in the control group will be given an electronic home exercise program (HEP) of proximal arm exercises developed by study therapists. They will be encouraged to exercise for 30 minutes a day with the electronic HEP (i.e. to match the duration with device). A supervising therapist will check in with all participants once per week to check on engagement with their exercise program and to troubleshoot any issues with device or the electronic exercise program. To measure compliance and quantify dose, the device will report the date, time, and number of repetitions completed for each movement type (stationary/overground) throughout the study using integrated electronics. Using technology, we previously developed for another study, the electronic exercise program provided to control participants will record how long the book is opened each day with a hidden magnetic sensor and data logger. Participants in both groups will continue therapy for the duration of their inpatient stays (average length of stay for individuals with moderate to severe impairment is 14 to 22 days, respectively, based on 104, n = 4142). The actual length of stay for each participant will be quantified and included as a covariate in the data analysis. Once participants are discharged, they will receive a post-therapy assessment and they may be allowed to keep the device and the exercise program based on the therapists' recommendations for the duration of the study. Participants will return three months following stroke onset for a final assessment. We would like to utilize the Tenovi Gateway device to collect the amount of use data. This data will be automatically uploaded to secure web portal through a Tenovi Gateway device, which plugs into the wall at subjects' rooms at the Acute Rehab Unit and or subjects' homes, automatically communicates with the exercise repetition counts through bluetooth, then uploads the data to the web portal through a low-speed cellular data connection. A study team member may visit participants' homes to set up the devices.

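### The primary model adjusts for an undefined treatment intensity measurable only after randomisation, and the plan gives two different primary methods

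*Combined protocol and SAP*

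**What the plan says.** The section on statistical methods for the aims assigns the primary outcome to a repeated-measures ANCOVA, whose purpose is "to account for any baseline differences between groups or variability in treatment intensity". It lists no covariates and does not say what intensity is. The Background & Purpose section also names RM-ANCOVA. The same methods section attributes the expected benefit to dose ("due to the increased dose of UE motor system activation") and gives repetitions a separate analysis: "we will test if this effect depends nonlinearly on the number of repetitions performed with the device".

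The chronological description of procedures adds: "The actual length of stay for each participant will be quantified and included as a covariate in the data analysis". No model is named or exempted.

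Asked directly for the method for the primary outcome, the plan answers "t-tests with Bonferroni corrections, or Wilcoxon rank sum tests if the distributions fail the Lilliefors test for normality". Under the next prompt, on secondary, post hoc or exploratory analyses, it says "The effect of treatment on each outcome measure will be assessed using a repeated-measures ANOVA". Neither answer mentions a covariate.

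The primary outcome is change from baseline under Primary outcome measure, but the 3-month score in the endpoint definition.

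**The concern.** An adjusted comparison estimates the effect of being assigned the device only if the covariates are fixed before assignment. Here the plan calls for adjustment for something that assignment may change and that the plan itself names as the route to benefit. Taken literally, this could remove part of the effect the trial is meant to detect. It also sits badly with the plan's modified intention-to-treat rule, which keeps everyone with follow-up data whatever their deviations from protocol.

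The second problem is choice. An analyst could follow the ANCOVA or the unadjusted tests, on change or on score, and cite the plan for each. Enrolment and procedures are complete and analysis is under way, so this choice may now be made with data in hand.

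**Working it through.** **1. What could treatment intensity mean?** The preset targets (1000 repetitions a day for device, 30 minutes a day for control) are constant within an arm, so they supply no variability between participants. What remains is device repetitions, control open-time and length of stay. Randomisation follows the baseline assessment, so all three are observed or completed after it. Repetitions are also a secondary outcome: "Number of exercise repetitions performed with device or exercise program".

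**2. Scale.** The sample-size section gives 29 per group, 80% power, alpha 0.05 and 10% dropout, but no SD or effect size. So 58 can only be back-solved: 29 × 0.9 = 26.1, about 26 evaluable per arm. For 80% power (two-sided t-test) this implies a standardised effect of 0.79. I assume an effect of 5.5 FM points and SD 7 (5.5/7 = 0.786). Unadjusted power is then 79% at 26 per arm, and 64% with the 37 participants in the renewal form (19 and 18, assuming all are analysed).

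**3. Adjusting for minutes per day.** This is the common scale the procedures suggest, since the control target was set "to match the duration with device". Assumed: device mean 30, control mean m, SD 10 in both arms, 0.2 FM points per minute, remainder of the effect direct.

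- Adjusted coefficient = 5.5 − 0.2 × (30 − m).
- Residual variance = 49 − 0.2² × 10² = 45, so residual SD is 6.71.
- SE ≈ 6.71 × √[2/26 + (30 − m)²/(50 × 100)].

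| Control minutes | Coefficient | SE | Power, 26 per arm | Power, 37 in all |
|---|---|---|---|---|
| 30 | 5.5 | 1.86 | 82% | 67% |
| 25 | 4.5 | 1.92 | about 62% | 48% |
| 20 | 3.5 | 2.09 | 38% | 28% |

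Power is simulated. With equal use the adjustment does no harm; the loss grows with the gap between arms.

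**4. Adjusting for length of stay, no device effect.** Assumed: stay and FM share an unmeasured severity factor U, with loading −0.5 on stay and r = 0.5 or 0.8 on FM; SD of stay 5 to 10 days. Bias = 0.5 × r × 7 / SD × (difference in stay).

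- No difference: no bias, type I error 5%.
- 2 days: 0.5 × 0.5 × 7/10 × 2 = 0.35 up to 0.5 × 0.8 × 7/5 × 2 = 1.12 points; type I error 5–9%.
- 4 days: 0.7 to 2.24 points; type I error 6–21%.

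**5. Method conflict.** Assumed: baseline FM uniform on 0–42 or truncated normal(20, 11); blocks of 4 within the plan's two FM strata; 3-month FM = slope × baseline + 5.5 × arm + normal(0, 7), slope 0.4, 0.7 or 1.0; n = 52 and 37. The share of trials in which an unadjusted t-test and a baseline-adjusted ANCOVA differ at p<0.05 is roughly 11–60% for the score and 1–34% for change. SD 7 here is what remains after baseline; in steps 3 and 4 it is the unadjusted within-arm SD. The two sets of figures are therefore not on one scale.

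**6. Change or score.** Change = score − baseline. With continuous baseline FM in the model, subtracting baseline lowers only the baseline coefficient, by 1; the arm coefficient is identical. With only the two-level stratum this fails. In the step 5 setting the two coefficients then differ by about 1.2–1.7 points on average, and verdicts disagree in about 20–30% of trials.

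**The case against.** The answer naming only t-tests or Wilcoxon tests may be a shortened form of the methods section, which uses those tests as follow-up comparisons to the RM-ANCOVA. That is plausible and softens the conflict. It does not remove it, because the question was the primary method and the answer omits both the ANCOVA and any covariate.

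The step 5 simulation does not test that answer exactly. It applies no Bonferroni factor, because none is stated, and has no Wilcoxon branch. The effect and SD are assumed; the only FM difference in the documents is 4.25. These points limit the figures, not the textual conflict.

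A reader might infer that the plan puts repetitions into the efficacy model and so would erase the device effect, with power near 5% if the effect were fully mediated. The documents do not support this. No section says repetitions enter that model, they have their own dose-threshold analysis, and the procedures describe only open-time for control. Only the outcome and data-collection lists suggest a control count.

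A reader might also infer that adjusting for length of stay biases the result. That needs assignment to change stay. The documents neither show nor exclude this, and the rationale ties discharge to payors and self-care.

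**Conclusion.** The concern holds as an unresolved specification of the sole primary comparison, not as demonstrated bias. Three things rest on the text alone: treatment intensity is undefined and its only varying measures come after randomisation; length of stay is a covariate with no model exempted; and the stated primary methods and outcome definitions differ.

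The consequences are conditional. Dose adjustment changes what is estimated if use differs by arm, because the plan names dose as the mechanism; the amount is unknown and can be nil. Length of stay matters only if it differs by arm because of assignment, and under the assumed correlations it takes about 4 days for a marked effect. The method conflict is the firmest part, because it can change the significance verdict whatever intensity means. Confidence is high on the text and moderate on the sizes.

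**What to change.** Reconcile the Background & Purpose, Primary outcome measure, endpoint-definition, statistical-methods and primary-method text to one primary analysis: the between-arm difference in FM at 3 months from an ANCOVA with continuous baseline FM as covariate. The randomisation stratum may be added but must not replace baseline FM. Change and score then give the same arm coefficient.

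Delete the reference to treatment intensity from the statement of what the primary model adjusts for, and take length of stay out of that model. Report dose and length of stay by arm, and use them only in analyses labelled exploratory, including the dose-threshold analysis.

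Date the change and make it before results by arm are seen, or disclose that it came later.

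The cost is small. No new data are needed. If stay is prognostic and does not differ by arm, dropping it raises the SE by about 2–8% under the assumed correlations (1.93/1.89 to 1.93/1.79), or 2–6 points of power, and less if baseline FM already carries that information. The outcome lists and the procedures should also be reconciled on what dose was recorded for control, though this does not affect the primary comparison once the fix is made.

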### Background & Purpose of Research

## Describe the purpose, specific aims or objectives and specify the hypotheses or research questions to be studied:

For this study, we hypothesize that use of movable wheelchair arm rest device during inpatient therapy will lead to significantly greater improvements in UE motor recovery than conventional treatment. (For a demonstration video of the movable wheelchair arm rest device, please visit: <https://youtu.be/RfbaOGhJfug>). Our Aim is to perform a randomized controlled trial of the movable wheelchair arm rest device with inpatients with subacute stroke in three different inpatient rehabilitation facilities (N=58; Months 6-24). UCI will be one of the study sites. Rancho Los Amigos Rehabilitation center and Casa Colina Hospital and Centers for Healthcare will potentially be the other two study sites. We are in the process of negotiating the contracts between sites. Participants will be >3 days and <3 weeks post-stroke, with initial FM scores <4239. Participants will be randomized to receive the movable wheelchair arm rest device or an electronic exercise program and instructed to practice moving their arm between therapy sessions. The primary outcome measure will be change in FM score from baseline to three-months post-stroke. We hypothesize that participants who receive movable wheelchair arm rest device will have significantly greater improvements in FM score than control ( $p < 0.05$ , RM-ANCOVA) without an increase in pain or spasticity, if they exceed the putative threshold of UE motor drive needed for recovery. Success Criteria: A significantly greater increase in FM of >4.25 points (the FM MCID40) between movable wheelchair arm rest device and control at three months.

At project end, we will have validated the clinical feasibility and efficacy of the movable wheelchair arm rest device and optimized it for production and mass distribution. If our plan is successful, we will have demonstrated that wheelchair-based "rocking therapy" can help patients routinely achieve the threshold level of sensory motor drive needed to provoke true UE recovery.

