**Movable wheelchair arm rest device group:** participants in this group will be provided with a wheelchair equipped with movable wheelchair arm rest device and will be trained by training therapists on how to use the device to perform stationery reaching practice and to help them move around using the overground mode. Training therapists can customize the range of motion needed for device's integrated electronics to count a "repetition" based on participant's ability. Once training therapists determine participants are competent to operate the device, they will be instructed to perform stationary reaching practice and to use the device to move around the inpatient facility with supervision from study personnel. A target dose of 1000 device "repetition" per day is encouraged. We estimated this will take about 30 minutes per day of device use at around 1 repetition every 2 second. Once participants are discharged from the unit, they will be allowed to keep the movable wheelchair arm rest devices until their 3-month post stroke follow up visit, the last visit of the study. Participants' utilization of the device will be supervised by therapists who have been trained in the device operation. Tenovi Gateway device will be used to collect the amount of use data. This data will be automatically uploaded to secure web portal through a Tenovi Gateway device, which plugs into the wall at subjects' rooms at the Acute Rehab Unit and subjects' homes. The Teniovi Gateway device will automatically communicates with the exercise repetition counts from the movable wheelchair arm rest through bluetooth, then uploads the data to the web portal through a low-speed cellular data connection.

**Control group:** participants in this group will be given an electronic exercise program designed by training therapists. These exercises will be assigned to the participants electronically using a commercial home exercise program platform commonly used by hospital systems (i.e.: Medbridge). They will be encouraged to exercise for 30 min/day in addition to the regular rehabilitation therapy at ARU. These exercises will be monitored and supervised by therapists who have been trained in the study protocol. Once participants are discharged from the unit, they will be allowed to keep the electronic exercise program until their 3-month post stroke follow up visit, the last visit of the study.

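### The plan treats a nonlinear dose-response as evidence of a dose threshold, but nonlinearity does not imply one, and no comparison that could examine the claim of benefit only above a threshold is written

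*Combined protocol and SAP*

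**What the plan says.** The statistical-methods answer under Study Design & Statistics sets out the dose analysis in four steps.

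- Data source: "Using data from the sensors on movable wheelchair arm rest device".
- Test: "we will test if this effect depends nonlinearly on the number of repetitions performed with the device".
- Restated as a hypothesis: "we hypothesize that the movable wheelchair arm rest device will provide a benefit only if the dose exceeds a threshold".
- Locating the threshold: "A key goal is to also identify that threshold (by making a graph for humans like the one for rats", closing a parenthesis there, with the stated aim of guiding clinical prescription and goal setting.

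Background & Purpose of Research makes the same condition part of the main hypothesis. Device users are to improve more than controls "if they exceed the putative threshold of UE motor drive needed for recovery".

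On control-arm exposure, the list of secondary outcomes includes "Number of exercise repetitions performed with device or exercise program". The chronological description of procedures says the control programme "will record how long the book is opened each day with a hidden magnetic sensor and data logger", which is a measure of time, not of repetitions. Neither passage links control exposure to the threshold analysis.

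**The concern.** The plan joins the test and the hypothesis as though one restated the other. They are different statements. A threshold is one kind of nonlinear curve. Saturation is another: the first repetitions bring most of the gain and later ones add little. Both depart from a straight line, so a significant departure cannot say which one is present.

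The hypothesis also has two halves: a gain over control above some dose, and no gain over control below it. The second half is a statement about low-dose device users relative to controls. No such contrast is written.

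The plan calls finding the threshold a key goal and means to base prescription and goal setting on it. A saturating response reported as a threshold would misdirect that use.

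**Working it through.** **1. Is there a plan figure to reproduce?** None for the dose analysis: no model, null hypothesis, test statistic or alpha. The only figure is for the arm comparison in Sample Size Determination: 29 per group, 80% power, alpha 0.05, 10% dropout. It gives no effect size or SD, so it can only be inverted.
- Evaluable per arm: 29 × 0.9 = 26.1, about 26.
- Standardised difference at 80% power, two-sided 5%: (1.960 + 0.842) × √(2/26) = 0.777; 0.792 by the exact t method.
- If the difference were the 4.25-point criterion, SD = 4.25/0.792, about 5.4.

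The renewal form reports 37 enrolled over all sites (2 + 12 + 23), or about 18 per arm if balanced.

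**2. Does nonlinearity identify a threshold?** Assumptions for illustration: the test is a quadratic term (the plan does not say so), dose is uniform on 0 to 1 of its maximum, and the maximum benefit is E = 8.5 FM points. The population quadratic coefficient for a curve f is 30 ∫ f(x)(6x² − 6x + 1) dx. For a step at c this equals −30·E·c(1 − c)(1 − 2c).

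| True curve | Threshold? | Quadratic coefficient |
|---|---|---|
| Saturating, 8.5 × 1.1x/(0.1 + x) | No | −10.7 |
| Step at 0.25 | Yes | −30 × 8.5 × 0.25 × 0.75 × 0.5 = −23.9 |
| Step at 0.50 | Yes | 0 |
| Step at 0.75 | Yes | +23.9 |
| Hinge at 0.50 | Yes | 30 × 8.5 × 0.0625 = +15.9 |

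The saturating curve departs from linearity with no threshold. A mid-range step shows no quadratic departure. An early step has the same sign as saturation, so looking at the sign does not settle it. Simulation agrees. With 5,000 users and SD 5.35, the saturating curve gives p of about 10⁻²⁹ and the mid-range step gives p = 0.84.

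With 26 users at SD 5.35, the same test is significant in 10–15% of runs under two saturating curves, 6% under the mid-range step, 16% under the hinge and 33% under the step at 0.75. These rates belong to the assumed test and curves. They are not properties of the plan.

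**3. What would a contrast of low-dose users with controls show?** Take low dose as the lower half of the range, so 13 users against 26 controls, or 9 against 18. The 95% half-width is t × SD × √(1/m + 1/n).
- 26 per arm, SD 5.35: 2.03 × 5.35 × 0.340 = 3.7 points.
- 18 per arm, SD 5.35: 2.06 × 5.35 × 0.408 = 4.5; 4.6 averaged over the random number of low-dose users.
- 26 per arm, SD 10: 2.03 × 10 × 0.340 = 6.9; 7.0 averaged likewise.

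In simulation with an 8.5-point maximum, this contrast detects a low-dose benefit as follows.

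| Setting | Saturating, no threshold | Mid-range threshold |
|---|---|---|
| 26 per arm, SD 5.35 | 87% | about 2% |
| 18 per arm, SD 5.35 | 72–73% | about 3% |
| 26 per arm, SD 10 | 39% | about 3% |

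It bears on the question as the nonlinearity test does not. Even so, an estimate near zero would exclude 4.25 points only in the most favourable setting.

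**4. Can the breakpoint be read off a graph?** With 26 users and no dose effect at all, the best-fitting step fell anywhere from 0.10 to 0.85 of the dose range (5th to 95th percentile). A breakpoint needs an interval.

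**The case against.** The strongest reply has three parts.

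*The plan may intend a threshold shape.* It ties the form to rodent meta-analyses and a specific graph, and the functional form may lie in those sources. This is a fair reading of intent, but the form is not in the plan, and the only test named is for nonlinearity.

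*Controls may be included.* A reader might infer that low-dose users will never be compared with controls. The documents do not say that. The effect whose dose-dependence is to be tested is, from the preceding sentence, the device-control difference, and the primary model is meant to account for treatment intensity. What stands is that no comparison with controls by dose is written.

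*Any error rate is the reviewer's.* A reader might also infer that the planned test usually misses a real threshold. That cannot be said, because no test is named and the rates move with the curve, SD and dose distribution.

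The reply also bears on the remedy. A formal rule might seem the answer: set controls at zero dose and claim a threshold when a hinge or step beats every other shape by 2 AIC units. It is not shown to be safe. With a useless device and a residual dose-prognosis correlation of 0.4–0.6 (assumed), simulation had it claim a threshold in about 17–50% of trials; under a straight line it did so in about 2–23% at 26 per arm. Controls are also encouraged to exercise 30 minutes a day, so they are not a clean zero dose of motor drive.

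**Conclusion.** The point holds as a gap between hypothesis and analysis. Nonlinear dependence does not imply a threshold, and the plan contains neither a comparison of shapes nor a contrast that examines the no-benefit-below half of the claim. This is a matter of logic and holds at any sample size and for any general test of nonlinearity.

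Its numerical size cannot be given as one rate. What can be said, under the assumed SDs and a mid-range split, is that the low-dose difference from control would be known to about ±3.7 to ±7.0 FM points. At 26 or about 18 per arm, the data will often not distinguish the shapes.

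The consequence is confined to the threshold aim, and the randomised comparison of arms does not depend on it. Dose is chosen by participants after randomisation, and the movement that counts as a repetition is set to each patient's ability. Better prognosis could therefore go with higher counts and mimic a threshold. The result is exploratory whatever model is used.

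**What to change.** In the statistical-methods text:

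1. State that nonlinearity alone will not be reported as evidence of a threshold.
2. Fit and report side by side constant, linear, saturating and threshold (hinge or step) models of 3-month FM, adjusted for baseline FM and for length of stay, which the procedures already name as a covariate. Give the control arm its own intercept, or add a sensitivity analysis without controls, because controls follow their own programme.
3. Report the breakpoint with a confidence interval, and the adjusted device-minus-control difference below it with its interval.
4. If the linear or saturating model fits about as well as the threshold model, say that the data do not distinguish the shapes. Do not turn the fit comparison into a pass/fail rule.
5. Label the whole analysis exploratory, giving self-selected dose and possible confounding with prognosis as the reasons. The renewal form says analysis is under way, so record when this text was added.

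The cost is a paragraph and a few model fits on data already collected. The downside is that a merely nonlinear result can no longer be presented as support for a threshold, and the honest answer will often be inconclusive.

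### The dose threshold meant to guide prescription is to be located from a graph of non-randomised repetitions, with no operational dose summary, adjustment, uncertainty measure or exploratory label stated

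*Combined protocol and SAP*

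**What the plan says.** The statistical methods item of Study Design & Statistics hypothesises benefit only above a dose threshold. It promises a test of whether the effect depends nonlinearly on device repetitions, with no model, contrast or alpha. For locating the threshold it says: "A key goal is to also identify that threshold (by making a graph for humans like the one for rats". The purpose follows: "which will enable us to move forward with effective clinical prescription and goal setting".

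The dose is what each device user achieves. Randomisation is to device or control, and the whole device arm shares one encouraged target of 1000 repetitions a day. The unit is set individually. The study design item says "Training therapists can customize the range of motion needed for" the electronics to count a repetition, and the chronological description in Project Procedures agrees: "The supervising therapist will customize the range of motion needed for" the same purpose.

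The two sections differ on use after discharge. In the study design item, "they will be allowed to keep the movable wheelchair arm rest devices until their 3-month post stroke follow up visit". In the chronological description, "they may be allowed to keep the device and the exercise program based on the" therapists' recommendations.

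Two adjustments appear, and neither is tied to the threshold. The RM-ANCOVA of the treatment effect on the primary outcome is "to account for any baseline differences between groups or variability in treatment intensity". The chronological description adds: "The actual length of stay for each participant will be quantified and included as a covariate in the data analysis". The item asking for post hoc and exploratory analyses answers only with a repeated-measures ANOVA.

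**The concern.** A graph can display a dose-response pattern. It does not fix a cut-point, say how uncertain that cut-point is, or separate the effect of dose from the reasons people reached it. Users who recover faster may do more repetitions because they are recovering. Counts are also not on a common scale when the counted range of motion follows ability.

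The repetitions are logged by date, time and movement type, so the raw data exist. What is missing is the summary to put on the horizontal axis: daily or total, inpatient or to three months, stationary, overground or both. Leaving that open until the data are in adds further choices to the choice of cut.

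The stake is the threshold statement. It is called a key goal and is meant to inform prescription, so an unstable cut-point could be reported as a target for patients.

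**Working it through.** **Inputs**
- Planned device users: 29 per group less 10% dropout (Sample Size Determination), 29 × 0.9 = 26.1, so 26.
- Actual device users: the renewal form gives 2 + 12 + 23 = 37 enrolled across the three sites, matching 22 men + 15 women. An even split is assumed, giving 18 or 19.
- Simulations are unadjusted with a normal outcome. These are assumptions, because the documents give no dose or outcome distribution.

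**The plan's own figure.** There is none for the threshold. The stated 58 is 2 × 29, and 26 / 0.9 = 28.9 rounds up to 29, so the dropout arithmetic is consistent. That calculation is for device versus control and says nothing about locating a cut-point.

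**1. How much the undefined dose window matters.**
- Inpatient only, over the cited 14-22 day stay: 1000 × 14 = 14,000 to 1000 × 22 = 22,000.
- Enrolment (over 3 days, under 3 weeks after stroke) to three months (90-91 days): 1000 × (90 − 21) = 69,000 to 1000 × (91 − 3) = 88,000.
- Ratio: 69/22 = 3.1 to 88/14 = 6.3.

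The second line assumes that the inpatient target continues after discharge. No post-discharge target is stated.

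**2. Spurious cut-points.** Order the n users by dose. For a cut with k users below and n − k above, with mean changes m1 and m2 and pooled variance s² on n − 2 degrees of freedom,

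t(k) = (m2 − m1) / √[s²(1/k + 1/(n − k))].

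Take the best cut and compare it with the ordinary t critical value. With at least 5 per side, k runs from 5 to n − 5: 10 candidate cuts at n = 19 and 17 at n = 26. Results with no dose effect (50,000 replicates):

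| n | favourable direction (nominal 2.5%) | two-sided (nominal 5%) |
|---|---|---|
| 19 | 10.4% | 20.6% |
| 26 | 13.1% | 26.6% |

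Repeat runs agree within about one percentage point. With 3 per side (20,000 replicates), the two-sided rates are 27.5% and 32.5%.

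**3. Imprecision when a threshold exists.** True step at mid-range, doses spread evenly, at least 3 per side. The central 95% of estimated cut-points covers these parts of the dose range:
- n = 26: 12% to 88% for a 0.8 SD step, 27% to 74% for a 1.6 SD step.
- n = 18: 14% to 86% and 22% to 79%.

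**4. Threshold or straight line?** A calibrated comparison (bootstrap from the fitted line, nominal 5%) detects a 1 SD step in 7.9% (n = 19) and 9.4% (n = 26) of trials, and a 1.5 SD step in 17.8% and 22.7%.

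**5. Confounding.** The documents give no correlation between dose and recovery, so its size is unknown and it could act in either direction. As an illustration only, suppose one prognostic factor correlates 0.3 or 0.5 with both dose and outcome. A best cut (3 per side, n = 26) is then nominally significant in about 36% or 56% of trials with no causal dose effect, against 33% without the factor.

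**6. What a remedy can deliver.** A permutation test that repeats the search restores the level: 2.6% and 5.3% (n = 19), 2.0% and 4.7% (n = 26), one- and two-sided. This was checked for the unadjusted version only. A percentile-bootstrap interval with at least 5 users per side is not a safe companion. For a 1 SD step, its nominal 95% coverage depends on where the true step lies in the dose range:

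| step at | 50% | 35% | 25% | 15% |
|---|---|---|---|---|
| n = 19 | 98% | 90% | 69% | 31% |
| n = 26 | 98% | 96% | 84% | 53% |

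The 5-per-side rule excludes cuts near the ends, so the interval can look informative and still miss.

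**The case against.** The strongest reply is that this is a secondary idea in a phase II trial. The threshold is not a listed outcome, a nonlinearity test is planned, a consultant will review all analyses, and no p-value is promised for the graph. Much of that is right. The nonlinearity test counts in the plan's favour, although it has no model and does not locate a cut. The 20-27% describes a substitute procedure and is not an error rate of the plan. What remains is that the same text calls the threshold a key goal and names prescription as its use. Review by a consultant is not a specification, and the imprecision in step 3 needs no p-value.

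A second reply is that the rodent graph being imitated may carry its own rule. It may, but that source is not part of these documents, so the claim is only that no rule is stated here.

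A third is that date-stamped logs show actual use whatever the retention rule was. That stands: the conflict over keeping the device does not block the analysis. It still affects what a three-month dose means and has to be reconciled.

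**Conclusion.** The point holds, at minor to moderate weight. The documents plan to locate a threshold for prescription from a graph of achieved, non-randomised repetitions counted on individual scales, and state no operational dose summary, adjustment, uncertainty measure or exploratory label for it. With 19 to 26 device users, a cut-point obtained this way can be spurious (about 20-27% against 5% under the best-cut stand-in) or can fall almost anywhere in the dose range when the true step is modest. The figures assume an even split of the 37 enrolled, normal outcomes and unadjusted models.

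A reader might infer three stronger things, and the documents support none of them.
- That the efficacy test depends on exceeding the threshold, because the hypothesis under Background & Purpose carries such a clause. The planned device-versus-control analysis and the 4.25-point success criterion are unconditional, so that clause is loose wording and the primary inference is unaffected.
- That the graph is the whole dose-response plan. A nonlinearity test is also stated.
- That dose is undefined altogether. The unit is named and logged; the analysis summary is what is missing.

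**What to change.** Write a dated addendum before the threshold analysis is run. The renewal form says data analysis is under way, so the addendum should say whether the graph has already been seen. It should:
- label the threshold analysis exploratory and associational;
- state that efficacy rests only on the as-randomised comparison, and that no above-threshold comparison supports efficacy or by itself sets a prescription;
- fix one dose summary (daily or total, window, movement types), and label any three-month total at 1000 a day as assuming that the inpatient target continues after discharge;
- report the dose-response plot with a fit of baseline-to-three-month FM change on dose within the device arm, adjusted for baseline FM and days of device exposure, with its confidence band;
- if a cut-point is reported, take its p-value from a permutation that repeats the search;
- give the range of cut-points compatible with the data over the observed doses, and say that thresholds near the ends cannot be excluded; do not present a percentile-bootstrap interval restricted to at least 5 users per side as a 95% interval;
- state that a device-arm fit describes association with dose and does not test benefit over control, that repetition counts are not on a common scale, that adjustment cannot remove confounding by recovery after baseline, and that the data probably cannot tell a threshold from a straight line.

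The study design item and the chronological description must be reconciled on keeping the device after discharge.

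The cost is a short addendum and a small analysis of data already collected, with no new visits. The downside is a weaker threshold statement.
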